#### 7.6.2.3. Adverse Events of Special Interest

Potential liver injury, ie, suspected and/or confirmed Hy's Law, DILI cases will be assessed as adverse events of special interest (AESI) and must be reported as SAE. Information of abnormal laboratory test results including the course and evolvement, clinical signs and symptoms, detailed medical history and concurrent medication, history and current lifestyle including alcoholic assumption, history of exposure to environmental chemical agents will be used to assess the case(s).

## 7.6.2.4. Relationship to Study Treatment

Liafensine is an investigational medicinal product (IMP). The causality relationship to liafensine for all AEs (serious and non-serious) will be assessed by the investigator. The causal relationship of an AE to the study treatment will be assessed as either:

#### Related

There is as at least a reasonable possibility that the drug caused the AE (ie, there is evidence or arguments to suggest a causal relationship between the drug and AE)

#### Unrelated

- Does not follow a reasonable temporal sequence from administration of drug
- Does not appear to worsen when the drug is re-administered
- There is not a reasonable possibility that the drug caused the AE
- An alternate etiology has been established, ie, the AE is more likely explained by another cause (eg, other study treatments or procedures, underlying medical conditions, concomitant medications, etc) than the study treatment.

## 7.6.2.5. Recording Adverse Events

Adverse events should only be recorded by an investigator or by a healthcare provider qualified by training and experience. Patients should be asked in an open-ended manner about the occurrence of AEs. All AEs are recorded in the electronic CRF (eCRF).

It is generally not necessary to record both a diagnosis and its associated symptoms and laboratory abnormalities. For example, if "acute renal failure" is recorded as an AE, "creatinine 5 mg/dL" need not be recorded.

If an AE necessitates a procedure, the description of the event (eg, appendicitis) rather than the procedure (appendectomy) should be listed as the AE.

Any ongoing AEs and SAEs should be followed during study visits until resolution, or until the event is otherwise explained or judged by the investigator as stable or no longer clinically significant (unless the patient is lost to follow-up or withdraws consent).

#### 7.6.2.6. Severity Assessment of Adverse Events

Adverse events will be reported, and severity graded, according to the following guidelines:

Mild	Awareness of signs or symptoms but easily tolerated
Moderate	Discomfort sufficient to cause interference with normal everyday activities
Severe	Incapacitating with inability to work or perform normal activities

In the event of the change in severity, the existing AE should be updated accordingly.

## 7.6.2.7. Reporting Adverse Events

All AEs regardless of causality will be recorded from the time a patient signs an ICF and through Follow-up period.

All SAEs regardless of causality will be recorded from the time a patient signs an ICF until 30 days after the last administration of study treatment. If SAEs are determined to be related to the study treatment by the investigators, these SAEs need to be reported beyond 30 days.

## 7.6.2.8. Serious Adverse Event Reporting Requirements

If an SAE occurs, the sponsor or designee is to be notified within 24 hours of investigator's awareness of the event. The time frame also applies to follow-up information on a previously reported SAE and pregnancies. This can be done by completing SAE entry through eCRF in the EDC. In the event of EDC outage, the investigator must complete the paper SAE reporting form and email or fax it to the sponsor or designee.

Investigators may be requested to obtain additional information on an SAE to allow for a complete assessment of the event.

Adverse event (serious and non-serious) reporting to regulatory authorities, including Suspected Unexpected Serious Adverse Reactions (SUSARs), will be carried out in accordance with applicable local regulations by the investigator, sponsor or designee.

All SAEs should be followed to resolution or stabilization.

## 7.6.3. Pregnancy Reporting

Pregnancy is not considered an adverse event. However, any patient who becomes pregnant during the study must be withdrawn from the study immediately. The investigator must report all pregnancies in the patient or partner of the patient within 24 hours of the investigator becoming aware of the event.

Pregnancy and maternal information will be collected until completion or termination of pregnancy including outcome of pregnancy and details of birth (if applicable).

If the outcome of the pregnancy meets the criteria for an SAE (eg. ectopic pregnancy, spontaneous abortion, intrauterine fetal demise, neonatal death, or congenital anomaly/birth defect) the investigator should follow the procedures for reporting SAEs.

#### 8. STATISTICS

Additional details of the analyses will be provided in the statistical analysis plan (SAP) which will be finalized prior to breaking the blind.

## 8.1. Study Design

This study will be conducted as a multicenter, a randomized, double-blind, placebo-controlled Phase 2b trial to assess the efficacy, safety, tolerability, and PK of liafensine. The primary endpoint is change in MADRS total score from baseline (Visit 3, Day -1) to Visit 7 (Day 42) in DGM4-positive patients. The primary analysis will be conducted to assess liafensine treatment effect for combined liafensine 1 mg QD and 2 mg QD doses vs placebo in randomized patients who are DGM4-positive.

## 8.2. Determination of Sample Size and Statistical Rationale

Eligible patients will be randomized 1:1:1 to receive liafensine 1 mg QD, liafensine 2 mg QD, or placebo QD. The primary analysis is to assess treatment difference in MADRS total score change from baseline (Visit 3, Day -1) to Visit 7 (Day 42) between the combined liafensine 1 mg QD and 2 mg QD doses vs placebo, in DGM4-positive patients. A sample size of forty-seven (47) randomized DGM4-positive patients per arm is sufficient to detect a 4.5-unit difference between the combined liafensine 1 mg QD and 2 mg QD treatment groups and the placebo treatment group in the change in MADRS total score from baseline to Visit 7 with 80% power at the 2-sided 0.05 alpha level, assuming a standard deviation of 9 units.

To compensate for potential loss of power due to randomized patients who do not take at least one dose of study drug or who do not have a post randomization efficacy evaluation (~5%), a total of approximately 150 DGM4-positive patients (50 DGM4-positive patients per arm) will be randomized.

To examine trend in the total patient population and in the subgroup of DGM4-negative patients in order to evaluate DGM4 as a potential biomarker for predicting response to liafensine, approximately 20% additional DGM4-negative patients (10 per arm, total 30) will also be randomized. The sample size of 30 randomized patients in the DGM4 negative group is not estimated based on formal statistics in terms of power and alpha level.

The sample size may be re-estimated/re-adjusted if more than expected missing data are observed at Day 42.

## 8.3. Statistical Methods

#### **8.3.1.** Analysis Population

The Full Analysis Set (FAS) includes all randomized patients who took at least one dose of study drug and had a post-randomization efficacy evaluation. The FAS population will be analyzed by treatment randomized regardless of the actual treatment received. The primary and secondary efficacy results of the study will be based on analysis in FAS patients with positive DGM4 biomarker. Safety Population includes all patients who took at least one dose of study drug. The Safety population will be analyzed by the actual treatment received regardless of treatment randomized.

## 8.3.2. Primary Estimand

The primary estimand, the main clinical quantity of interest to be estimated in the study, is defined by the following three components:

- Population: patients with treatment-resistant depression with the DGM4-positive biomarker
- Endpoint: change in MADRS total score from baseline to Day 42
- Measure of Intervention: the effect of the initially randomized treatment that would have been observed had all patients remained on their treatment throughout the double-blind phase

The primary analysis will be based on the full analysis set, as described above, and the MADRS total scores collected during the double-blind treatment period.

## 8.3.3. Efficacy Analyses

The primary efficacy endpoint is the change in MADRS total score from baseline (Visit 3, Day -1) to Day 42 (Visit 7). The primary efficacy analysis will be performed in DGM4-positive patients at 2-sided significance level of 0.05 using a mixed model for repeated measures (MMRM) that includes the fixed effects of treatment, visit (categorical covariate), treatment-by-visit interaction, baseline MADRS total score (continuous covariate), and region. An unstructured variance-covariance matrix will be used. The least-squares (LS) mean change in MADRS total score at Day 42 from baseline for the combined liafensine treatment arms (1 mg QD and 2 mg QD) and placebo arm will be estimated from the MMRM model. The treatment effect for the combined liafensine treatment arms vs placebo will be estimated using the LS mean difference at Day 42 from the MMRM model. The comparison of the change in MADRS total score from baseline to Day 42 between each of the 2 liafensine treatment arms and placebo will be carried out using the same approach. The key secondary efficacy endpoint for this study is the change in CGI-S from baseline (Visit 3, Day -1) to Day 42 (Visit 7), in DGM4-positive patients.

Other secondary and exploratory efficacy endpoints include the CGI-I, SDS, response (defined as  $\geq$  50% improvement from baseline in MADRS total score at Day 42), and remission (defined as MADRS total score  $\leq$  10 at Day 42), in DGM4-positive patients. CGI-S, CGI-I, and SDS will be analyzed using the same MMRM model as for the primary efficacy endpoint. Response rate, remission rate, and corresponding 95% confidence interval (CI) for each treatment group will be derived by using Clopper-Pearson method. The comparison of response rate and remission rate between treatment groups will be carried out using the Cochran–Mantel–Haenszel (CMH) test.

Subscales, individual items, and domains of endpoints will also be analyzed in an exploratory manner, using the same MMRM model as for the primary efficacy endpoint.

The change in MADRS total score from baseline in DGM4-negative patients will be analyzed using the same approach as described for the primary endpoint analysis in the DGM4-positive patients. The LS mean of the change in MADRS total score for each treatment group and the treatment difference in DGM4-negative patients will be estimated. The treatment effects between the DGM4positive and negative patients will be compared primarily in descriptive fashion to examine the trend, and may be evaluated by including the interaction of DGM4 status and treatment group in the mixed model.

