3.6. Stratified Analysis

Efficacy analyses will be stratified by biomarker status and region. Details are presented under the analysis for each endpoint.

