5.4.1.2. Main Estimator

The primary efficacy analysis will be performed in DGM4-positive patients at 1-sided significance level of 0.05 using MMRM with imputation based on the MAR assumption. The model will include the fixed effects of treatment, visit (categorical covariate), treatment-by visit interaction, treatment by baseline MADRS total score, baseline MADRS total score (continuous covariate), and region. Change from baseline in weekly visits at Days 7, 14, 28, and 42 will be

the repeated outcome measures, and the model will use an unstructured variance-covariance matrix. If the model does not converge the algorithm (Lu 2010) will be used to assist in the convergence.

The following hypothesis will be tested based on the test statistics from the mixed model:

 $H_0: u_i - u_0 = 0 \text{ vs. } H_A: u_i - u_0 \neq 0$

where u_i is the expected mean change from baseline in MADRS for liafensine at Day 42 and u_0 is the expected mean change from baseline in MADRS for placebo at Day 42. In H₀ and H_A above, i = 1, 2, 3 are for liafensine 1 mg, 2 mg, and both arms pooled, respectively, for implementing the closed testing procedure described in Section 3.7. The LSMESTIMATE statement in SAS Mixed procedure will be used to test the global null hypothesis of no treatment difference between both active arms and placebo while keeping all 3 treatment groups separately. Please see sample SAS code in Appendix 8.2.

The LS mean for change from baseline in MADRS total score at Day 42 for the combined liafensine treatment arms (1 mg QD and 2 mg QD) and placebo arm will be estimated from the MMRM model. The comparison of the change in MADRS total score from baseline to Day 42 between each of the two liafensine treatment arms and placebo will be carried out using the same approach. Separate figures with the mean change (\pm SD) and LS mean change (\pm SE) by visit will be displayed.

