5.6. Exploratory Analysis

5.6.1. Treatment Response in DGM4-Positive Patients

Treatment response is defined as \geq 50% improvement from baseline in MADRS total score at Day 42 (Visit 7) in DGM4-positive patients. Response rate and corresponding 95% confidence interval for each treatment group will be derived by using Clopper-Pearson method (Clopper 1934). The comparison of response rate between treatment groups will be carried out using the CMH test. The percentage of subjects achieving response in MADRS by visit will be displayed in a bar chart.

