5.6.2. Remission in DGM4-Positive Patients

Remission is defined as MADRS total score ≤ 10 at Day 42 (Visit 7) in DGM4-positive patients. Remission rate will be analyzed using the same methodology as described in Section 5.6.1. The percentage of subjects with remission by visit will be displayed in a bar chart.

5.6.3. Change in MADRS Anhedonia Subscale and Individual Items from Baseline to Day 42, in DGM4-Positive Patients

Change in MADRS anhedonia subscale and individual items from baseline (Visit 3, Day -1) to Day 42 (Visit 7) will also be analyzed in an exploratory manner, using the MMRM model without imputation similar to the one used in sensitivity analysis (2) for the primary efficacy endpoint described in Section 5.4.1.3. Anhedonia score is the sum of MADRS items 1 (reported sadness), 2 (apparent sadness), 6 (concentration difficulties), 7 (lassitude), and 8 (inability to feel).

5.6.4. Change in MADRS Total Score from Baseline to Day 42, in DGM4-Negative Patients

The change in MADRS total score from baseline to Day 42 (Visit 7) in DGM4-negative patients will be summarized using descriptive statistics.

5.6.5. Change in MADRS Total Score from Baseline to Day 42 in Liafensine 1 mg QD Group and 2 mg QD Group, in both DGM4-Positive and DGM4-Negative Patients

The change in MADRS total score from baseline to Day 42 (Visit 7) in liafensine 1 mg and 2 mg QD groups in both DGM4-positive and DGM4-negative patients will be analyzed using descriptive statistics. The treatment effects between the DGM4-positive and negative patients will be compared primarily in descriptive fashion to examine the trend and may be evaluated by including the interaction of DGM4 status and treatment group in the mixed model.

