8.8. SAS Code for Stratified CMH Test

*** CMH test for pooled analysis stratified by region;

- *** gpn=3: both active arms pooled, gpn=4: placebo arm;
- *** For 1 mg vs. placebo and 2 mg vs. placebo, replace 3 with 1 and 2, respectively.;
- proc freq data=adqs4(where=(gpn in (3 4) and dgmn=3 and avisitn=70));
- table region*GPN*aval / CMH ALPHA=0.10;

run;

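### Remission, a fixed Day 42 score, is compared without baseline MADRS: a small, cheaply recovered loss of precision on an exploratory endpoint

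*Protocol*

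**What the plan says.** - **Test.** Protocol 8.3.3: "The comparison of response rate and remission rate between treatment groups will be carried out using the" CMH test. SAP 5.6.1: "The comparison of response rate between treatment groups will be carried out using the CMH test". SAP 5.6.2: "Remission rate will be analyzed using the same methodology as described in Section 5.6.1". None of these places names strata or a baseline covariate.
- **Strata.** The general rule in SAP 3.6 is "Efficacy analyses will be stratified by biomarker status and region". Among DGM4-positive patients biomarker status is constant, so that rule reduces to region. The sample code in SAP 8.8 carries the comment "CMH test for pooled analysis stratified by region" and the statement "table region*GPN*aval / CMH ALPHA=0.10".
- **Endpoint.** SAP 5.6.2: "Remission is defined as MADRS total score ≤ 10 at Day 42 (Visit 7) in DGM4-positive patients". Response is a fall of at least half from the patient's own baseline.
- **Primary model.** SAP 5.4.1.2 includes "baseline MADRS total score (continuous covariate), and region" and adds a treatment-by-baseline term. Protocol 8.3.3 also adjusts for baseline MADRS and region. SAP 5.6.3 uses the same family of models for the anhedonia subscale and single items.
- **Status.** Response and remission are exploratory in both documents, with nominal p-values outside the multiplicity procedure (protocol 8.3.3.1; SAP 3.7).

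**The concern.** Remission is a fixed end score, so its probability depends on where the patient starts. As an illustration, a patient at 28 needs an 18-point fall to reach 10, and a patient at 40 needs 30 points. Randomisation is stratified by DGM4 status and region, not by severity. Entry sets a HAMD-17 floor but no MADRS total-score range. The arms can therefore differ by chance in starting MADRS.

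The primary analysis absorbs such a difference and the remission comparison does not. At stake are some precision on a result that clinicians read easily, and the chance that remission appears to disagree with the adjusted primary result only because a covariate was left out.

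**Working it through.** **1. The plan's own figure.** Inputs from protocol 8.2: difference 4.5, SD of change 9, 2-sided 0.05, 80% power, 2:1 for pooled active v placebo. Placebo n = (1.96 + 0.84)² × 9² × (1 + 1/2) / 4.5² ≈ 47.1, or 48 rounded up, against 47 stated; power at 47 is 79.9%. Then 47 / 0.95 ≈ 50 per arm, as planned. This figure concerns the MADRS change and does not depend on the present point. No figure is given for remission.

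**2. Inputs for remission.** From the documents: 100 active v 50 placebo, difference 4.5, SD of change 9, cut-off 10. Assumed, because the documents do not give them: mean baseline MADRS 33, mean placebo change −11, baseline SD 4 to 6, slope of Day 42 score on baseline 0.5 to 1.0.

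**3. Hand check at baseline SD 5, slope 0.8.**
- Mean Day 42 score: placebo 33 − 11 = 22; active 22 − 4.5 = 17.5.
- Residual variance 81 − (0.2 × 5)² = 80. Day 42 SD = √(80 + (0.8 × 5)²) = √96 = 9.80.
- Remission: placebo Φ((10 − 22)/9.80) = 11.0%; active Φ((10 − 17.5)/9.80) = 22.2%.
- SE of the difference = √(0.222 × 0.778/100 + 0.110 × 0.890/50) = 6.1 points.
- SE of chance baseline imbalance = 5 × √(1/100 + 1/50) = 0.87 points.
- Change in remission per baseline point: active 0.8 × φ(0.765)/9.80 = 2.43 points; placebo 0.8 × φ(1.225)/9.80 = 1.54 points. On average one third of an imbalance arises in the larger arm and two thirds in the smaller, so a 1-point imbalance shifts the difference by 2.43/3 + 2 × 1.54/3 = 1.8 points.
- Share of variance due to imbalance = (1.8 × 0.87 / 6.1)² ≈ 7%.

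**4. Simulation, 1,500 trials per setting.** Unadjusted risk difference and region-stratified CMH test, against logistic regression on treatment, region and baseline MADRS with its standardised risk difference. Power is for remission at 2-sided 0.05, with a Wald test for the logistic model. The variance ratio is adjusted/unadjusted.

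| Baseline SD | Slope | Remission, active v placebo | Variance ratio, remission | Shift per 1-point imbalance, unadjusted | Power, CMH v logistic | Variance ratio, response |
|---|---|---|---|---|---|---|
| 4 | 0.5 | 20.2% v 8.9% | 0.996 | 1.1 points | 42.5% v 39.1% | 1.011 |
| 4 | 1.0 | 22.2% v 11.0% | 0.959 | 2.0 points | 38.5% v 38.9% | 0.986 |
| 5 | 0.5 | 20.2% v 9.2% | 0.975 | 1.5 points | 38.7% v 36.7% | 1.016 |
| 5 | 1.0 | 23.4% v 12.0% | 0.936 | 2.0 points | 36.7% v 39.2% | 0.995 |
| 6 | 0.5 | 20.2% v 9.2% | 0.947 | 1.4 points | 39.9% v 37.6% | 1.013 |
| 6 | 1.0 | 24.4% v 13.4% | 0.887 | 2.1 points | 35.9% v 39.5% | 0.971 |

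Slope 0.8 gave remission ratios of 0.985, 0.939 and 0.893 for SD 4, 5 and 6; the middle value agrees with the hand check. After adjustment the shift was at most 0.4 points. One SD of imbalance is 0.7 to 1.05 points, so a typical shift is about 0.8 to 2.2 points against a simulated SE of 5.7 to 6.5. A second run of 3,000 trials per setting gave shifts of 1.1 to 2.5 points and remission variance ratios of 0.997 to 0.861.

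**5. Choice of test.**
- Like for like at 2-sided 0.05, adding baseline moved power from 38.7% to 39.8% (Wald) and 45.4% to 46.1% (likelihood ratio) at weak correlation. At SD 5, slope 1.0, it moved from 34.7% to 40.4% and from 41.4% to 45.5%.
- Under no effect at 1-sided 0.05, CMH rejected 4.1–4.4%, the adjusted likelihood-ratio test 5.2–5.7%, and a test on the adjusted risk difference 6.7–6.9%.
- A Firth fit with a Wald test rejected 2.7–3.4% under no effect, with power 51–54% against 52–58% for CMH.

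**The case against.** The strongest reply is that nothing here is an error. Randomisation keeps the CMH test valid, and chance imbalance is noise that its error rate already reflects. Remission carries a nominal p-value, and the baseline-adjusted primary analysis of the same scale carries the inference. SAP 5.1.3 tabulates baseline MADRS, so an imbalance will be visible. Choosing between CMH and a covariate model is a question of efficiency. All of this stands, and it confines the point to precision.

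Three further objections also stand:
- Response has baseline built into its definition, so the point does not extend to it.
- The sizes rest on assumed baseline values, and the HAMD-17 floor of 21 at screening and baseline may narrow the spread.
- The region-only stratum is inferred. SAP 8.8 is not labelled for response or remission, filters on dgmn=3 where the DGM4-positive code in 8.1 uses dgmn=1, fits the CGI-I test of 5.4.3 equally well, and is offered for reference only.

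One objection stands only in part. Against CMH, the adjusted Wald test ranges from about 3 points less power to about 4 points more, so a free gain in power is not established. The loss at weak correlation comes from the Wald form: like for like, adding baseline did not lower power. Conversely, part of the apparent advantage of a likelihood-ratio test over CMH comes from its higher rejection rate under no effect.

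**Conclusion.** The point holds for remission, as a modest loss of precision. Adjustment would cut the variance of the remission difference by about 0–11% (up to about 14% in one run). It would also remove a shift of roughly 1 to 2.5 percentage points per point of baseline imbalance, against a standard error of about 6 and a simulated difference of about 11. These sizes depend on the assumed baseline mean, spread, slope and placebo change; weak correlation puts the gain near zero.

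A reader might infer more, and the documents do not support it:
- **Bias or an invalid test.** Allocation is randomised, so imbalance is chance and the CMH error rate holds.
- **The same loss for response.** Response is scaled to each patient's baseline, and its variance ratio stayed between 0.96 and 1.02 across runs.
- **A reason to drop CMH.** A gain in power over CMH at equal error rates was not shown.
- **A threat to the trial's conclusion.** Remission is exploratory and lies outside the testing procedure.

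**What to change.** - **SAP 5.6.2:** for DGM4-positive patients, add a logistic model for remission with treatment, region and baseline MADRS. Report the standardised risk difference with its confidence interval, pooled and for each dose v placebo, and state how the interval is computed. If a p-value is given, use a likelihood-ratio or penalised-likelihood test and not a Wald test.
- **SAP 5.6.1:** keep the CMH test as the planned hypothesis test for both endpoints, and state that it is stratified by region.
- **Response:** the same model is optional, for consistency only.

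The cost is a paragraph and a few lines of code, using a baseline score already collected, and it should be fixed before unblinding. The downside is a model fitted with few placebo remissions (about 5 to 6 of 50) and a slightly liberal small-sample error rate. Keeping the CMH test covers this. The handling of missing Day 42 scores is a separate matter and is not changed by this addition.
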